## 4. Selection of Participants and Clinical Sites/Laboratories

### 4.1. Rationale for Study Population

Asthmatics will be studied as the relevant target for RV-induced asthma exacerbations and compared to control and AR subjects to identify the basis for their unique sensitivity. We will study mild asthmatics who are well-controlled with or without long-term controllers and low risk insofar as they have no recent (3-year) history of exacerbations to mitigate the risk of a severe asthma exacerbation during the study. It is our contention that it is the innate response to RV-infected *nasal* epithelium that is the relevant target of inquiry and, as such, **that AR subjects will behave identically to asthmatics**, however, in their case, the absence of relevant addressins and chemotaxins in their lungs precludes development of a lower airway response. We will therefore also enroll AR subjects to validate this concept that both asthmatic and AR cohorts will display increased circulating mediators of inflammation, but that only in asthmatics will

this translate to increased lower airway inflammation. Results will be evaluated in comparison to a non-allergic non-asthmatic control cohort and we will consider the potential impact of asthma long-term controllers regarding modulation of measures of airway mediators and markers of inflammation.

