#### 4.3. Exclusion Criteria (all subjects)

Individuals who meet any of these criteria are not eligible for enrollment as study participants:

1. Positive test for serum neutralizing antibody to RV16 at enrollment visit ( $\geq 1:8$ )(Visit 1).

2. Upper airway modified Jackson criteria symptom scores  $\geq 7$  at time of inoculation.
3. Chronic heart disease including bradycardia, lung diseases other than asthma, or other chronic illnesses including epilepsy, peptic ulcer disease, thyroid disease, urinary tract obstruction, vagotonia, autoimmune disease, primary or secondary immunodeficiency or any household contacts who are known to be immune deficient. Any medical conditions that could be adversely affected by the administration of cholinergic agent.
4. Any use of nasal corticosteroids, LT modifiers, omalizumab, within 4 weeks prior to Visit 1.
5. Current use of  $\beta$ -blockers or cholinesterase inhibitors (for myasthenia gravis)
6.  $\beta 2$ -agonist use  $\geq 4$  days/week in any week or  $\geq 2$  nights during the month before Visit 1.
7. Recent (within 3-yr) asthma exacerbation requiring urgent care visit (unless the treatment involved only the use of a bronchodilator), hospitalization, or oral CCS
8. Intubation or management in the ICU for an asthma exacerbation ever.
9. An upper or lower respiratory tract infection within 2 months prior to enrollment.
10. Previous nasal or sinus surgery within the last 12 months
11.  $>5$  pack-year smoking history or any smoking within the past 6 mos.
12. Hemoglobin  $<11.5$  g/dL for non-African American subjects or hemoglobin  $< 11.0$  g/dL for African American subjects detected at Visit 1.
13. Laboratory values (other than hemoglobin and ANC) measured at Visit 1 that are considered to be of clinical relevance by the Investigator.
14. Absolute neutrophil count (ANC)  $<1500$  cells/mm^3 (or 1.5 K/ $\mu$ L) or absolute lymphocyte count (ALC)  $<800$  cells/mm^3 detected at Visit 1.
15. Use of investigational drugs within 12 weeks of participation
16. Past or current medical problems or findings from physical examination or laboratory testing that are not listed above, which, in the opinion of the investigator, may pose additional risks from participation in the study, may interfere with the participant's ability to comply with study requirements or that may impact the quality or interpretation of the data obtained from the study.

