The results from experimental challenges in asthmatics with RV-16 and RV-39 at the University of Virginia indicate that RV challenges can be done safely in mild asthmatics who are not using anti-inflammatory medications. This has also been the experience of others using the RV challenge model elsewhere. In addition, RV challenges have also been performed on mild/moderate persistent asthmatics who are very well controlled on long-term controllers (inhaled corticosteroids with or without long-acting  $\beta$ -agonists) without untoward reactions.(58) In our first study of asthmatics enrolled in challenge studies at the University of Virginia using RV-39, one of 19 subjects needed intervention with inhaled steroids during peak cold symptoms (47). One college student enrolled in our studies needed a short course of oral steroids when challenged with RV-39 produced under GMP conditions. This student was one out of 23 asthmatic subjects who were inoculated with this pool in our experimental challenges. Additionally, 3 of the last 12 asthmatic subjects challenged with this pool of RV-39 more recently used albuterol more frequently for chest symptoms during peak symptoms, but they experienced no significant declines in their FEV1 values monitored at home or observed in our clinical research center. No subject enrolled in any of our studies who have been challenged with either RV-16 or -39, or in studies published by others using RV-16 that we are aware of, has experienced an exacerbation requiring hospitalization or treatment in the ER. In our previous published study with RV-16 prior to the virus being manufactured under GMP conditions, 13 of the 16 subjects with mild asthma reported mild symptoms of cough, wheeze, or chest discomfort during the infection, but none required intervention with anti-inflammatory medications such as inhaled or oral corticosteroids (1). We are interested to use this new pool because the majority of published data from experimental challenges with RV have been done using RV-16, which is helpful in comparing our results (e.g., (8, 31)).

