All subjects in the proposed study will be inoculated with RV-16 and monitored daily for 4 days following inoculation in the clinical research center at UVA hospital and again on day 7 dpi. Daily monitoring will include upper and lower respiratory symptoms scores, and FEV1 measurements (using a hand held FEV1 monitor given to each subject), which will be recorded twice daily (morning and evening) on diary cards. Subjects will also be recording the number of puffs of albuterol used daily from metered dose inhalers. In addition, monitoring each morning will include a physical examination focused on the respiratory tract, along with spirometry and measurements of expired nitric oxide (FeNO). This monitoring will be done to enhance our ability to detect changes during the acute infection and to ensure safety. The research team member will be a licensed physician or nurse and will be readily available should any problems occur. Thus far, no significant problems or serious adverse events have occurred for any of the asthmatics inoculated with either RV-16 or RV-39. The inclusion of mild-/moderate-persistent asthmatics who are very well controlled on inhaled CCS could lead to more severe exacerbations. However, this has not been the experience of other research groups enrolling this population (58). Furthermore, as noted, the average American has 4 respiratory infections/yr and we would argue that as none of these subjects will have had even a modest asthma exacerbation in the previous 3 years (over which time they will on average have had 12 RV infections) we do not feel this modification adds an untoward risk to the study. And that the current safety monitoring criteria will continue to suffice.

As for any adverse long-term safety effects of an experimental RV-16 infection, the cold symptoms observed have been generally similar to, but a bit shorter in duration than a natural RV infection (see above). Because most adults will

experience at least one or two viral induced colds a year, it would be very difficult to differentiate any adverse effects of an RV-16 experimental infection from the effects of a subsequent natural respiratory tract infection in an effort to evaluate any safety problems long-term.

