## **5.2. Risks of Investigational Product or Intervention cited in Medical Literature**

Recently, in European studies, challenges with RV-16 were well-tolerated by subjects with moderately severe asthma who were treated with inhaled corticosteroids (9, 59) . However, asthmatic subjects in those studies were using inhaled steroids at the time of inoculation, which would interfere with our goals of judging the effects of RV infection on lower respiratory tract symptoms and bio-markers of inflammation.

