## **Appendix 1: Treatment Guidelines for Asthma Symptom Exacerbations**

### **Treatment guidelines should symptom exacerbations occur during the study:**

If a study participant experiences an increase in lower respiratory tract symptoms, or a decline in lung function, the following plan describes how subjects will be treated.

- For FEV1 value dropping between 20-29%20% from the baseline value not responding to albuterol, start on inhaled corticosteroids (Flovent 110 mcg./puff, 2 puffs bid) and discontinue when symptoms return to baseline.
- For FEV1 value dropping between 30- 49% from the baseline value not responding to albuterol, check oximetry and start on inhaled corticosteroid as above and 3 to 5 days of oral steroids (Prednisone 50 mg/day).
- For FEV1value dropping 50% or more from the baseline value. Transportation to the emergency room will be recommended and arranged. Individual stopping rules will apply as described in the Complete Clinical Protocol (Section 8.1.2). Further follow-up and management with the subject's primary care doctor; [name] and his study team will continue to be involved and available for follow-up and evaluation 30 days afterward for any subject who requires oral steroids, a visit to the ER, or hospital admission.

These treatment plans are in keeping with recommendations from the *Guidelines for the Diagnosis and Management of Asthma* (60).

**Note:** Baseline FEV1 values apply to the FEV1 measurements established at the scheduled visit with 2 days of RV-16 inoculation. Also note that young adults rarely become febrile during a natural or experimental infection with rhinovirus. However, if subjects develop a temperature greater than or equal to 101 degrees F, [name], together with back-up from the allergy fellow on call will be contacted (paged) for evaluation.\

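### Sections 4.1 and 5.1 admit asthmatics on stable inhaled steroid, but Section 7.3 prohibits the drug without exception, and Appendix 1's 20-29% step does not say what happens to their controller

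*Combined protocol and SAP*

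**What the plan says.** **Who is admitted.** Section 4.1 states: "We will study mild asthmatics who are well-controlled with or without long-term controllers". It adds that "we will consider the potential impact of asthma long-term controllers regarding modulation of measures of airway mediators and markers of inflammation". Section 5.1 shows what such controllers are when it describes challenges in "mild/moderate persistent asthmatics who are very well controlled on long-term controllers (inhaled corticosteroids with or without long-acting" beta-agonists). It then turns to this study: "The inclusion of mild-/moderate-persistent asthmatics who are very well controlled on inhaled CCS could lead to more severe exacerbations". It goes on to report that other groups enrolling such patients have not seen this, and concludes: "And that the current safety monitoring criteria will continue to suffice".

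**Who is excluded.** Exclusion 4 in Section 4.3 reads: "Any use of nasal corticosteroids, LT modifiers, omalizumab, within 4 weeks prior to Visit 1". ICS and LABA are not listed.

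**What is prohibited.** Section 7.3 lists inhaled corticosteroids and LABAs among the prohibited medications. It gives no exception for a baseline controller and no washout. Section 11.2(5c) makes ICS use a reason for which a participant may be terminated. Section 12.2.1 makes treatment with an inhaled corticosteroid a trigger for recording an adverse event. Section 5.2 says of European challenge studies that "asthmatic subjects in those studies were using inhaled steroids at the time of inoculation, which would interfere with our goals".

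**What the rescue plan does.** For a 20-29% FEV1 fall, Appendix 1 says: "not responding to albuterol, start on inhaled corticosteroids (Flovent 110 mcg./puff, 2 puffs bid) and discontinue when symptoms return to baseline". At 30-49% it adds oximetry and 3 to 5 days of prednisone 50 mg/day. At 50% or more it arranges transport to the emergency room.

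**The concern.** The eligibility text and the operational text describe different asthma cohorts. A subject on a stable ICS can meet every criterion in Sections 4.2 and 4.3 and still be taking a prohibited drug at inoculation. The site then has no rule for whether to continue the controller, stop it, or treat its use as a departure from the protocol.

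The first steroid step of the rescue plan has the same problem. Its instruction to begin a drug and later withdraw it describes someone who was not taking that drug. Two things are at stake: a clear instruction for a subgroup that the protocol itself singles out as a possible safety question, in a study that deliberately infects volunteers; and a single consistent definition of the asthma cohort that enters all three primary comparisons.

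**Working it through.** The plan gives no figure to reproduce on this point. The check is a comparison of sections, with one dose calculation.

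1. **Are ICS users really admitted?** Five pieces of text agree that they are.
   - Section 4.1 includes controller users.
   - Section 5.1 identifies controllers as ICS, alone or with LABA.
   - Section 5.1 discusses including such patients in this study and calls it a modification.
   - Exclusion 4 omits ICS.
   - In Section 4.2 the allergic rhinitis criteria rule out long-term controllers over the last 6 years, while the asthma criteria contain no such item.

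   The intention in Section 4.1 to weigh the effect of controllers on airway mediators makes sense only if subjects are taking them during the study.

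2. **Does the operational text allow them?** Section 7.3 does not: ICS and LABA are prohibited without qualification. Section 5.2 gives a scientific reason against ICS at inoculation, which contradicts Section 4.1. Sections 11.2(5c) and 12.2.1 mention ICS without separating a stable controller from a newly started drug.

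3. **What does the 20-29% step give an ICS user?** The dose is 110 mcg × 2 puffs × 2 times daily = 440 mcg/day of Flovent. There are two readings:
   - *Add-on:* the subject keeps the controller, receives a further 440 mcg/day, and stops only the addition on recovery. This is an escalation.
   - *Literal:* ICS is the thing started and ICS is the thing stopped. Flovent may then take the place of the controller, and recovery ends inhaled steroid altogether.

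   Appendix 1 does not choose between them.

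4. **How far does the gap extend?** At 30-49% the prednisone course applies whatever the subject was taking before, and at 50% so does the emergency-room referral. The ambiguity therefore belongs to the 20-29% step.

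5. **How many subjects?** The planned asthma cohort is 20 of 60. No section says how many will be on ICS, so the range is 0 to 20, at most 20/60 = one third of enrolment.

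**The case against.** **Section 7.3 may mean that there will be no ICS users.** If so, Appendix 1 needs no change. But Sections 4.1 and 5.1 are then wrong and exclusion 4 is incomplete. One side has to be edited in either case.

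**The step can be read as an add-on.** This is fair. Appendix 1 names a specific drug and dose, and nothing in it mentions stopping a baseline controller. A reader might infer that an ICS user gets no escalation before a 30% fall; the documents do not support that. Section 7.4 lists prednisone as rescue with no FEV1 threshold, Section 5.3 foresees short oral courses for more serious exacerbations, Section 7.1.1 keeps prednisone at the site, and subjects have a respiratory examination and spirometry on days 1 to 4. What remains is an unclear instruction.

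**Section 11.2(5c) is aimed at newly needed drugs.** That is its best reading, and termination is permissive. A reader might infer that every ICS user is terminable from day 0 and that 5c, with replacement under Section 11.3, determines who makes up the 20 asthmatics. No section says that stable users will be removed. The conflict with Section 7.3 does not depend on that inference.

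**ICS users have been challenged safely.** Section 5.1 reports this from other groups, and Section 5.2 reports good tolerance in moderately severe asthma treated with ICS. This stands against any claim of raised risk, but it does not supply the missing instruction.

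**Can an event probability be attached?** It is tempting to use the 1 in 45 asthmatics in Section 1.3 who wheezed with an FEV1 fall. She received RV-39, the size of her fall is not reported, and she was given oral steroid, which is the 30-49% treatment. Section 5.1 also reports 1 of 19 in an RV-39 study who needed inhaled steroid. Neither is described as an ICS user, and the number of ICS users here is unknown. No probability is supported.

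**Conclusion.** The conflict holds in the current text and should be resolved. Sections 4.1 and 5.1 admit stable ICS users (with or without LABA), and Section 7.3 prohibits what they take. The poor fit of Appendix 1's 20-29% step follows from that conflict and goes no further than that step. Its practical size depends on how many of the 20 asthmatics use ICS, which the documents do not state.

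The conclusion assumes that Sections 4.1 and 5.1 express the present intention. The wording of 5.1 suggests that controller users were added later and that Sections 5.2 and 7.3 and Appendix 1 were not brought into line; that explanation is an inference. The documents do not show that ICS users lack treatment, that they will be removed, or that they face a higher event rate.

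**What to change.** If controller users are to stay, as Sections 4.1 and 5.1 intend:

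1. **Section 7.3**, add: *A stable inhaled corticosteroid, with or without LABA, documented at Visit 1 is permitted and continued; starting or increasing one is prohibited except as rescue per Appendix 1.*
2. **Sections 11.2(5c) and 12.2.1**: limit the ICS trigger to a new start or a dose increase. The systemic-steroid trigger in 12.2.1 stays as it is.
3. **Appendix 1, 20-29% step**, add: *If already on inhaled corticosteroid, continue the controller and add the Flovent dose above; on recovery stop only the added Flovent.*
4. **Section 5.2**: remove or reword the statement about ICS so that it agrees with Section 4.1.

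If an ICS-free cohort is intended, add inhaled corticosteroids to exclusion 4 (Section 4.3 and the Synopsis) and delete the controller text in Sections 4.1 and 5.1. Appendix 1 can then stand.

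Bringing prednisone forward to the 20-29% step is not recommended. It is a debatable clinical choice with no basis in the documents, and if the exacerbation were classed as severe it could trigger Section 11.2(5b) and the enrolment halt in Section 12.8.2.2.1.

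Either route costs a few lines and leaves the sample size unchanged. The first keeps any ICS effect on mediators inside the asthma group, which Section 4.1 already accepts; the second narrows recruitment.
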